#### 2.2.2. Secondary endpoints

1. The change from baseline to 24 weeks in the natural logarithm of the mean of the 24-hour SDS profile for A4 (calculated in the same way as the primary endpoint).
2. The presentation of 17-OHP and A4 by individual baseline treatment strata in the study will be presented in the same manner as the primary endpoint (using 24-hour SDS profile at 24 weeks).
3. 17-OHP and A4 levels at 09:00 as a responder analysis (i.e. the number of subjects achieving results in the optimal or reference range respectively).
4. Changes relative to standard glucocorticoid replacement therapy in body composition (DEXA) (fat mass, lean mass and total bone density) to be measured at all sites except Germany.

#### 2.2.3. Safety endpoints

1. Routine haematology, biochemistry, physical examination, vital signs, urinalysis, electrocardiogram (ECG).
2. Clinical adverse events (AEs) – particular note of use of sick day rules and Addisonian crises. Under or over-replacement with glucocorticoids will be considered in the efficacy endpoints.
3. Changes relative to the standard treatment in weight, body mass index (BMI), waist circumference, and blood pressure (BP).

### 2.3. Statistical hypotheses

#### 2.3.1. Primary hypothesis

The primary comparison of interest is to test the null hypothesis  $H_0$ : There is no difference between the mean change from baseline to 24 weeks in the primary efficacy variable (the natural logarithm of

the mean of the 24-hour SDS profile for 17-OHP) in Chronocort® compared to standard glucocorticoid replacement therapy, versus the alternative hypothesis  $H_1$ : There is a difference in the mean change from baseline to 24 weeks in the primary efficacy variable in Chronocort® compared to standard glucocorticoid replacement therapy. The difference analysed will be the mean of the primary efficacy analysis variable for Chronocort® minus the mean of the primary efficacy analysis variable for standard glucocorticoid replacement therapy. This means that a negative difference will be in favour of Chronocort®.

### 2.3.2. Secondary hypotheses

For the secondary endpoint of the change from baseline to 24 weeks of the logarithm of the mean of the 24-hour SDS profile for A4, the same hypothesis as the primary analysis will be tested, with A4 in place of 17-OHP.

The responder analysis will test the null hypothesis  $H_{01}$ : The odds of response for Chronocort® is the same as the odds of response for standard glucocorticoid replacement therapy i.e. the odds ratio is 1, versus the alternative hypothesis  $H_{11}$ : The odds of response for Chronocort® is different to the odds of response for standard glucocorticoid replacement therapy. An odds ratio of greater than 1 favours Chronocort®. Response is defined as the number of subjects achieving results in the optimal or reference ranges (See 10.6). The hypothesis will be tested separately for 17-OHP and A4.

For the secondary endpoint of the change from baseline in body composition (DEXA), the results from the three tests: fat mass, lean mass, total bone density will be analysed separately. The results from each test will be used in turn to test the null hypothesis  $H_{02}$ : There is no difference between the mean change from baseline to 24 weeks in the result for Chronocort® compared to standard glucocorticoid replacement therapy, versus the alternative hypothesis  $H_{12}$ : There is a difference in the mean change from baseline to 24 weeks in the result for Chronocort® compared to standard glucocorticoid replacement therapy.

### 2.3.3. Multiple testing strategy

There will be no adjustment for multiple testing as the primary analysis will be considered the main analysis with the secondary and exploratory endpoints intended as support for the primary analysis.

## 2.4. Exploratory objectives, endpoints and hypotheses

The purpose of this document is to set out the primary, secondary and safety analyses, however several exploratory objectives will also be addressed in this study. The following were specified in the protocol, other analyses may be added on an ad hoc basis.

### 2.4.1. Exploratory objectives

- To assess the efficacy of Chronocort® with regard to the effect on testosterone levels over the 6-month treatment period.
- To assess the impact of Chronocort® on cardiovascular (CV) risk (evaluated using high-sensitivity C-reactive protein [hsCRP]).
- To assess the impact of Chronocort® on bone markers of serum C-terminal cross-linked telopeptide (CTX type I) and osteocalcin (after fasting).
- To assess changes from baseline in glucose and insulin in the morning (after fasting)
- To assess changes from baseline in glycated haemoglobin (HbA1c)
- To assess changes from baseline in plasma renin activity (PRA) in the morning.

- To assess the impact of Chronocort® on quality of life (QoL) using SF-36®, Multidimensional Assessment of Fatigue (MAF), and EQ-5D™.
- To assess subject compliance in subjects treated with Chronocort® over a 6-month period.

#### 2.4.2. Exploratory endpoints

1. Partial AUC of 17-OHP at 15:00-23:00, 23:00-07:00, and 07:00-15:00 (all refer to actual clock time of sampling).
2. The primary endpoint measure will also be presented for the profiles measured at 4 and 12 weeks for the purposes of titration.
3. Changes relative to standard treatment in the following:
  - a. Bone markers – serum CTX and osteocalcin (after fasting)
  - b. hsCRP
  - c. Assessment of glucose and insulin in the morning (after fasting)
  - d. Assessment of HbA1c, total testosterone, and PRA in the morning
  - e. QoL using SF-36®, MAF, and EQ-5D™
4. Use of glucocorticoids at beginning and end of the study will be presented both as individual glucocorticoids used, and as calculated hydrocortisone equivalents using accepted conversion constants for the calculations.

### 3. Study design

This study is designed as a parallel arm, randomised, open-label study, including dose titration and admissions for four overnight stays for 24-hour endocrine profiles. It will compare the efficacy, safety and tolerability of Chronocort® with standard glucocorticoid replacement therapy in the treatment of CAH over a treatment period of 24 weeks.

An overview of the study plan is illustrated in Figure 1. Written informed consent for the study will be obtained from subjects who have been stable on their current treatment for a minimum of 6 months. Subjects will be screened and entered in the study provided they meet the inclusion/exclusion criteria. 120 subjects will be randomised into this study to obtain 102 evaluable subjects (individual sites should not recruit more than 25 subjects without first consulting the sponsor). The randomisation either to Chronocort® or to continue on their original therapy will be stratified with regard to the subject's prior treatment:

1. Hydrocortisone only
2. Prednisone or prednisolone, alone or in combination with hydrocortisone
3. Dexamethasone only or in combination with any other glucocorticoid

[figure not shown]
Dose titration decisions will be made within two weeks of each profiling visit at weeks 4 and 12 using a standard titration algorithm after the subject has been re-admitted for 24-hour profiles that include 17-OHP and A4. These decisions will be made by a central independent physician, blinded to the treatment arm to minimise bias. The actual treatment change will be made by the local investigator. The independent blinded physician will determine either that no change is required or that an increase/decrease in the morning/midday/evening medication is needed. In the event that a change in the midday dose is advised for a subject who is receiving Chronocort or in a subject who is receiving twice daily dosing of standard therapy, the local investigator must decide to make this dose change at the most appropriate timepoint in their judgement (morning or evening), in addition

to any changes already advised for morning and evening doses, so that the total change advised is accommodated within the day.

Subjects completing the study will become eligible for an open extension study, in which all subjects will be offered Chronocort®.

Figure 1: Overview of DIUR-005 Study Schema

## 4. Timing of planned analyses

### 4.1. Data Review Meeting

The sponsor will convene a Data Review Meeting after the data has been cleaned and the database locked but before analysis has commenced. The review will be performed within the framework of the requirements of the ICH Guideline E9. The datasets used in the review will be masked to treatment allocation and dummy treatment groups with generic treatment labels will be used. The terms of reference for the Data Review Meeting are outlined in Section 13.10 of the protocol.

### 4.2. Interim analyses

No formal interim analysis is planned.

### 4.3. Final analysis

The final analysis will take place after the Data Review Meeting described in Section 4.1.

## 5. Sample size considerations

A sample size of 102 subjects provides greater than 95% power and 2-sided alpha 5% to demonstrate a fall in the logarithm of the mean 24-hour unsigned SDS of 17-OHP relative to the standard glucocorticoid replacement therapy group. It is assumed that (i) the mean fall in the Chronocort® group will be the same (0.78) as that observed in the phase II study (DIUR-003) (ii) the mean fall in the standard therapy group will be 0.2 (approximately 25% of the Chronocort® phase II study fall) and (iii) the standard deviation of the fall (0.681) is that seen in the phase II study. The study is powered to ensure that there can be a reasonable description of the comparison of Chronocort® with a variety of standard therapies. 120 subjects will be randomised to this study which will account for an inevaluability rate of 15%. Individual sites should not recruit more than 25 subjects without first consulting the sponsor.

## 6. Analysis populations

### 6.1. Full analysis set

The full analysis set comprises all subjects who were randomised into the study, who received at least one dose of Chronocort® or standard therapy, and who had at least one evaluable post-randomisation 17-OHP 24-hour hormone profile.

Subjects in the full analysis set will be analysed according to the actual treatment received (the first dose of treatment they actually took post randomisation).

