4. Care will be taken not to dose adjust for the Chronocort® arm of the study at baseline by selecting the initial dose following randomisation on the equivalent glucocorticoid dose at baseline, rather than basing it on hormone levels or symptoms. By using this method both arms will effectively continue on their baseline glucocorticoid dosage.

5. The primary endpoint is an objective biochemical measure that is not subject to bias in its ascertainment.
6. Efforts will be made to ensure that all subjects remain in the study and are evaluable. Subjects completing the study will become eligible for an open extension study, in which all subjects will be offered Chronocort® (this will be conducted under a separate protocol).
7. The statistical analysis plan (SAP) will be completed before randomisation of the first subject to the study.
8. There will be rigorous monitoring of sites to ensure compliance with all study procedures.
9. Treatment will be allocated using block randomisation. The block size will be determined by an independent statistician and will not be communicated to the study team.

Written informed consent for the study will be obtained from subjects who have been stable on their current treatment for a minimum of 6 months. Subjects will be screened and entered in the study provided they meet the inclusion/exclusion criteria. 120 subjects will be randomised into this study (see Subject Stratification below) to obtain 102 evaluable subjects (individual sites should not recruit more than 25 subjects without first consulting the sponsor).

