#### 10.2.2 Packaging and Labelling

Chronocort® capsules are contained within either a PVC/PE/PVdC blister pack sealed with aluminium lidding foil or a high-density polyethylene (HDPE) bottle sealed with a polypropylene (PP) lid. Each blister pack contains 10 capsules of the same dose strength. Each bottle pack contains 100 capsules of the same dose strength. The sponsor will supply Chronocort® to the pharmacy at the study site as clinical packs containing 100 capsules of each dose strength, i.e. 10 x 10-count blisters (100-count pack) or 1 x 100-count bottle. A treatment pack for each subject randomised to Chronocort® will be assembled by the pharmacy using the required number of clinical packs according to the individual subject prescription. Each dose

strength will be identifiable by the unique colour hard gelatin capsule and product/dose identifier printed on the capsule.

Chronocort® Treatment pack 1 will be dispensed by the study site pharmacy on Day 2 and taken home by the subject. Treatment pack 1 consists of a cardboard carton containing one clinical pack of each dose strength (5, 10 and 20mg Chronocort®), with each pack containing 100 Chronocort® capsules. The initial Chronocort® dose regimen will be determined according to the individual subject prescription, based on the hydrocortisone dose equivalent of the subject's previous therapy, with the hydrocortisone dose calculated as prednisone dose multiplied by 5 and dexamethasone dose multiplied by 80 (up to a maximum starting dose of Chronocort® 30mg, split as 20mg at night and 10mg in the morning).

Treatment pack 2 (dispensed at Visit 2 after 4 weeks) and Treatment pack 3 (dispensed at Visit 3 after 12 weeks) will be dispensed by the study site pharmacy. Treatment packs 2 and 3 will be assembled based on individual prescribed dosing regimen, including any dose adjustment required.

Chronocort® will be labelled as shown in Appendix 9. The subject number will be written on the study pack by the pharmacist.

Diurnal will also provide appropriate labels for the standard glucocorticoid replacement therapy that the pharmacy can use to label the drugs dispensed to subjects (See Appendix 9). The subject number will be written on the study pack by the pharmacist. The batch numbers of the standard glucocorticoid replacement therapy must be recorded by the pharmacist.

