### 6.2. Efficacy evaluable set

The efficacy evaluable analysis set comprises all subjects who were randomised into the study, who received at least one dose of Chronocort® or standard therapy, and who have an evaluable week 24 17-OHP 24-hour hormone profile, and who have no major protocol violations.

It is difficult to conduct trials in this indication. This is the first comparative trial of a re-formulation of a standard therapy for CAH. The efficacy evaluable analysis set is therefore the primary analysis set for the evaluation of efficacy. The robustness of the conclusions will be assessed by repeating key efficacy analyses using the full analysis set.

The final determination of the membership of analysis sets will be made at a Data Review Meeting convened by the sponsor before database lock.

Subjects in the efficacy evaluable set will be analysed according to the actual treatment received.

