### **10.2. Protocol deviations**

Any deviations from the protocol will be reviewed at the Data Review Meeting following trial completion but prior to database lock. Each protocol deviation will be classified as either 'minor' (unlikely to affect trial outcomes) or 'major' (likely to affect outcomes). Any subject considered to have a major protocol deviation will be excluded from the Efficacy Analysis set (See 6.223). In addition, protocol deviations will be grouped into the following high-level categories:

- Inclusion criteria – subject failed to meet all inclusion criteria,
- Exclusion criteria – subject met at least one exclusion criteria,

---

 This differs from the +/- 10 minute window specified for investigators in the protocol so that results within a wider window can be considered acceptable for analysis.

- Study procedure – site or subject did not follow procedures specified in protocol,
- Titration – site or subject deviated from the titration process,
- Treatment – IMP not taken as per protocol,
- Local sampling – site performed endocrine sampling locally.

Protocol deviations will be listed and summarised by randomised treatment group, classification (major or minor) and protocol deviation category.

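### SAP 6.1 groups the full analysis set by the first dose taken, so the named robustness check can itself depart from the randomised comparison (minor; nearly free to fix)

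*SAP*

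**What the plan says.** SAP 6.1 defines membership of the FAS (randomised, dosed, at least one evaluable post-randomisation 17-OHP profile) and then sets the grouping: "Subjects in the full analysis set will be analysed according to the actual treatment received", explained in parentheses as "the first dose of treatment they actually took post randomisation".

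SAP 6.2 makes the efficacy evaluable set primary. It requires an evaluable week 24 profile and no major violation, and it uses the same grouping phrase: "Subjects in the efficacy evaluable set will be analysed according to the actual treatment received". The same section names the check on this choice: "The robustness of the conclusions will be assessed by repeating key efficacy analyses using the full analysis set".

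Nothing elsewhere overrides the rule. Protocol 13.2 and 13.6 define the sets and the FAS repeat but not the grouping. SAP 10.5, 10.6 and Appendix A repeat the efficacy analyses in the FAS without altering it. The one SAP output stated by allocation is the deviation summary in SAP 10.2: "Protocol deviations will be listed and summarised by randomised treatment group".

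**The concern.** The evaluable set drops subjects for things that happen after randomisation: a missing week 24 profile or a major deviation. The FAS repeat is meant to show that the result does not depend on those exclusions. It does this best when its groups are the ones randomisation formed.

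The trial is open label, so a subject who starts on the other treatment does so knowing the allocation, and that choice may be related to outcome. Moving such a subject to the other arm brings a post-randomisation choice into the check as well. The likelier case is a Chronocort-randomised subject who stays on standard therapy, because Chronocort is supplied by allocation (Protocol 10.2.2: "A treatment pack for each subject randomised to Chronocort® will be assembled by the pharmacy"). At stake is the value of a supportive analysis, not the primary result.

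**Working it through.** **Inputs.** SAP 5 and Protocol 13.8 give mean falls of 0.78 (Chronocort) and 0.20 (standard therapy), SD 0.681, two-sided alpha 5%, 102 evaluable and 120 randomised. The allocation ratio is not stated; Protocol 8 says only "Treatment will be allocated using block randomisation". I assume 1:1 and 60 per arm in the FAS, which is its upper bound. Differences below are in falls, so positive favours Chronocort.

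**The plan's own figure.** With 51 per arm, SE = 0.681 × √(2/51) = 0.135 and 0.58/0.135 = 4.30. Power is 99.0% (normal) or 98.9% (t), consistent with the stated figure of more than 95%. Also 102/(1 − 0.15) = 120. The grouping rule does not affect the sample size.

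**Planning effect.** Let k Chronocort-randomised subjects stay on standard therapy, with mean fall m = 0.20 + d × 0.681.

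- As randomised: ((60 − k) × 0.78 + k × m)/60 − 0.20
- As treated: 0.78 − (60 × 0.20 + k × m)/(60 + k)

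For k = 3 and d = −1, m = −0.481. As randomised: (44.46 − 1.443)/60 − 0.20 = 0.517. As treated: 0.78 − (12 − 1.443)/63 = 0.612.

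| k = 3, refusers' mean | As randomised | As treated | Gap |
|---|---|---|---|
| 1 SD worse than the standard mean | 0.517 | 0.612 | +0.095 |
| 0.5 SD worse | 0.534 | 0.596 | +0.062 |
| at the standard mean | 0.551 | 0.580 | +0.029 |
| 0.5 SD better | 0.568 | 0.564 | −0.004 |
| 1 SD better | 0.585 | 0.548 | −0.037 |

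For k = 1 the gaps are +0.032 (1 SD worse), +0.010 (at the mean) and −0.013 (1 SD better). The gap of 0.029 at the standard mean is ordinary dilution from non-adherence, not selection. SE = 0.681 × √(2/60) = 0.124, so even the smallest difference is 0.517/0.124 = 4.2 SE from zero.

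**No drug effect.** Let each arm hold k subjects of the refusing type, all with outcomes shifted by the same number of SDs. As randomised they balance and the bias is zero. Dropping those in the Chronocort arm from the primary set gives a bias of (k/60) × shift × 0.681. Moving them to standard therapy in the FAS gives 2k/(60 + k) × shift × 0.681. For k = 3 and 1 SD these are 0.034 and 0.065. The as-treated check therefore errs in the same direction as the exclusion it is meant to test, and by more.

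The relevant consequence is that the primary analysis and the FAS repeat both falsely favour Chronocort. Simulated probabilities (unadjusted t-tests, Chronocort-arm refusers dropped from the primary set):

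| | FAS as treated | FAS as randomised |
|---|---|---|
| k = 1, 0.5 to 1 SD worse | about 2.6% to 3.0% | 2.2% to 2.4% |
| k = 3, 0.5 to 1 SD worse | 3.2% to 4.3% | 2.2% to 2.4% |
| k = 3, 1 SD better | 0.6% | 1.2% |

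The as-randomised range covers both values of k. The planned model is ANCOVA with baseline and prior therapy; these joint figures were not obtained under it.

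**The case against.** The strongest reply is that this is a latent gap in a supportive analysis. Discordant starters may not exist. In the primary set they would probably be removed in any case, since SAP 10.2 says "Any subject considered to have a major protocol deviation will be excluded from the Efficacy Analysis set", and grouping a set without major violations by treatment received is ordinary practice. Discordant starters could also be traced from planned outputs: deviations are listed individually, and SAP 11.1 lists exposure in detail. All of this stands, and it is why the point is minor. It does not remove the gap: exclusion as a major deviator applies to the evaluable set and not to the FAS, and it is decided at the Data Review Meeting.

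A reader might infer more than the documents support:

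- *That the trial's type I error is inflated.* For k = 3 at 1 SD worse, the as-treated repeat alone has a two-sided error of 7.4%, and 6.9% of null trials falsely favour Chronocort. Those rates belong to the repeat by itself under an unadjusted t-test. Protocol 13.6.1 makes every analysis other than the primary one secondary or exploratory, so the repeat carries no claim alone.
- *That the rule favours Chronocort.* It does so only if refusers do worse. If they do 1 SD better, it works against Chronocort.
- *That a Chronocort subject who takes a usual standard dose between randomisation and 23:00 would be relabelled.* The literal words of 6.1 allow it, but SAP 9.3.1 places the first dose of randomised treatment that evening, so this is unlikely to be the intent.

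**Conclusion.** The point holds as a minor one. The plan states no efficacy comparison as randomised, and the FAS repeat, its named check on the evaluable-set result, is expressly grouped by first dose taken. The effect is nil if every first dose matches allocation. With three discordant Chronocort-randomised subjects, the planning-effect estimate moves by +0.095 to −0.037 depending on whether they do 1 SD worse or better, and the conclusion is unchanged. Under no drug effect, the chance of a false primary result that the repeat appears to confirm rises by at most about two percentage points (4.3% against 2.2%). That case needs three such subjects in each arm, all a full SD worse. The counts, the shifts and the 1:1 ratio are assumptions, not figures from the documents.

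**What to change.** In SAP 6.1, replace the as-received rule with one sentence: *each full analysis set subject is counted in the arm to which he or she was randomised, whatever was taken first.* Add to the analysis-population summary, by randomised arm, the number of subjects whose first dose differed from allocation. The listings would allow this to be worked out, but a single row shows at once whether the issue arises.

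Optionally, use the same grouping in SAP 6.2. This changes nothing if discordant starters are excluded as major deviators, and it covers the case where the Data Review Meeting keeps one. Leave the safety-set rule in SAP 6.3 as written.

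The cost is one sentence (two with the option) and one table row, with no new data and no change in sample size. The result is grouping by allocation, not full intention-to-treat, because the FAS still requires a dose and an evaluable profile.
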